A randomized controlled trial comparing cosmetic outcomes of pediatric laceration closure using a tissue adhesive (Dermabond™) versus adhesive strips (Steri-Strips™) versus absorbable sutures

Study Protocol

NCT ID: NCT03280628

Document Date: 8/10/2017

Principal Investigator:
[name], MS
Vanderbilt University Medical Center
Pediatric Emergency Medicine
[name]
[name]

Table of Contents		
Section	Topic	Page
I	Specific Aim and Study Hypothesis	3
II	Summary of Approach	3
III	Background	3
IV	Rationale	4
V	Inclusion and Exclusion Criteria	4
VI	Subject Recruitment and Enrollment	4
VII	Study Procedures	5
VIII	Predictor Variables	5
IX	Outcome Variables	6
Χ	Ethical Considerations	7
ΧI	Risks of Study Participation	7
XII	Reporting of Adverse Events or Unanticipated Problems involving Risk to Subjects or Others	7
XIII	Study Withdrawal or Discontinuation	7
XIV	Data Management	8
XV	Statistical Considerations	8
XVI	Privacy and Confidentiality Issues	8
XVII	Follow-up and Record Retention	9
XVIII	Data Safety and Monitoring Plan	9
XIX	References	9

I. Specific Aim and Study Hypothesis

Specific Aim: The specific aim of this study is to determine the best of 3 different methods of closure of simple pediatric lacerations in terms of cosmetic outcome, pain, need for sedation, cost and length of ER stay.

Hypothesis: We hypothesize that the closure of simple pediatric lacerations with either a tissue adhesive (DermabondTM), or adhesive strips (Steri-StripsTM) will provide clinically equivalent cosmetic outcomes to absorbable sutures while reducing pain, need for sedation, cost and length of ER stay without increasing the risk of complications.

II. Summary of Approach

To address the Specific Aim we will conduct a 3-arm randomized controlled trial comparing methods of closure of simple pediatric lacerations. The 3 arms will be: DermabondTM, Steri-StripsTM, and absorbable sutures (our control arm).

We will examine the association between closure method and the primary outcome variable, cosmesis of the resultant scar.

As a secondary aim we will assess for statistically significant differences in the degree of pain experienced by the patient, in the need for sedation, in the cost of each closure method, and in the length of the patient's ER stay. We anticipate that the treatment arms (DermabondTM, Steri-StripsTM) will demonstrate no clinically significant difference in cosmetic outcomes while reducing the pain experienced by patients during laceration closure, reducing the need for sedation, reducing costs and reducing the length of patients' ER stays.

III. Background

Lacerations are a very common presentation in pediatric Emergency Departments (ED). In fact, over the past 2 years (February 2015-2017), there were a total of 3100 lacerations repaired in the ED at Monroe Carell Jr's Children's Hospital at Vanderbilt (VCH). This can be a painful and traumatic procedure for children, especially young children. Given that most lacerations occur in young children (74.1% in those less than 6 years old), it is important to use noninvasive and painless closure methods when possible. ^{10, 11, 15}

Historically, sutures have been the preferred method of closure for lacerations.¹⁸ While they have been made of different materials over the years, the general concept of needle and string has remained mostly consistent.¹⁸ However, new methods of wound closures have been developed since. Surgical tape was first developed by surgeon Horace Day in 1845.⁵ The earliest versions of surgical tape had several issues including proper adhesion, skin irritation, blocking of perspiration, etc.⁵ The modern version of surgical tape that we are now familiar with (Steri-StripsTM) has been around since the 1960s, and except for a few minor modifications, it has largely gone unchanged.³⁵

Tissue adhesives, derived from cyanoacrylate, were invented in the 1940s and have been used for decades for wound closure outside of the United States.³ However, it wasn't until 1998 that the Food and Drug Administration approved 2-octyl cyanoacrylate (DermabondTM) for use in the United States.³⁶

Despite the availability of both adhesive strips and tissue adhesives, a large study at an urban ED showed that while tissue adhesives are more likely to be used in children compared to adults, especially in facial lacerations, they are still wildly underused.³¹ In fact, out of the 3100 lacerations repaired at VCH, only 108 (3.5%) lacerations were closed using tissue adhesives, and none were closed with surgical tape exclusively. This is surprising given that tissue adhesives are very versatile (they have even been used to close tongue lacerations and nail bed injuries), and

have good tensile strength.^{6, 13, 28} Whether the clear preference for traditional sutures is due to a lack of knowledge or confidence in alternative methods remains unclear.

IV. Rationale

The aim of this study is to compare different methods of pediatric laceration closure. Although Steri-Strips[™] and other surgical tapes have been available for decades, there are few studies looking at their use in pediatric lacerations. ^{26, 34} Tissue adhesives such as DermabondTM have also been largely understudied, though this may be due to the fact that they are a relatively newer addition on the market. In fact, a metanalysis in 2008 examining the use of tissue adhesives for simple traumatic lacerations found only 11 applicable studies, with only 6 using exclusively pediatric patients, only 5 using Dermabond™ and some studies not using validated scoring systems.^{1,7} Most studies have used older versions of tissue adhesives, had small sample sizes or were used on iatrogenic lacerations (laparoscopic trocar incisions for example).^{2, 4, 9, 19, 22, 24, 27,} ^{29, 30} Two studies compared cosmetic outcomes of scars closed with Dermabond TM versus Steri-StripsTM but neither study used sutures as controls.^{26, 34} In addition, preliminary studies show that tissue adhesives and surgical tape are less costly and may lead to less sedation, which in turn can lead to decreased length of stay in the ED.8, 14, 20, 21, 25, 33 The proposed study will provide a definitive cosmetic comparison of two alternatives to suturing for pediatric lacerations while examining the patient/parent experience in terms of pain, cost and length of ED stay in the hope that this will allow for improvement in clinical care.

V. Inclusion and Exclusion Criteria

a. Inclusion criteria

- i. Age 0 to <18 years
- ii. Parents speak English
- iii. Chief complaint of laceration
- iv. Single, linear laceration
- v. Laceration less than 5 cm in length and 0.5 cm in width
- vi. Laceration less than 12 hours old
- vii. Laceration minimally contaminated (no visible dirt in wound)

b. Exclusion criteria

- i. Significant medical history that may impact wound healing (hematologic or oncologic diagnosis requiring chemotherapy, ichthyosis, epidermolysis bullosa, etc.)
- ii. Use of oral steroids (more than 5 days in the past month)
- iii. History of keloid formation
- iv. Allergy to tissue adhesives, adhesive strips, or topical anesthetics
- v. Lacerations requiring deep sutures
- vi. Lacerations caused by animal bites or scratches
- vii. Lacerations located on the scalp, eyebrow, eyelid, lip, mucosa, joint or nail
- viii. No access to photographic capabilities (camera or smartphone) and/or email, or unable to return to the VCH ED to have a picture taken

VI. Subject Recruitment and Enrollment

We will enroll a sample of 90 children and adolescents 0 to <18 years of age. All eligible patients will be recorded in the Screening Log (see Appendix I).

Subject identification and enrollment will be performed by trained study staff stationed in the VCH ED. The study staff enrolling the patient will obtain written informed consent and/or

assent, as applicable (see Consent Form and Assent Forms). Study staff will also complete a

Subject Enrollment Form (see Appendix II) and Subject Data Form (see Appendix III) which will be maintained in a locked file in the ED.

Institution/Hospital: Vanderbilt Children's Hospital

VII. Study Procedures

Study Design

The study design will be a single-blind, randomized controlled trial. After enrollment, all participants will have LET placed and their wound washed out with sterile normal saline.

Depending on which arm they are randomized to, participants will have their laceration closed by either DermabondTM, Steri-StripsTM, or absorbable sutures per the treatment arm protocols (Protocols, see Appendix IV). Unfortunately, given the nature of the study, neither the patient, parent nor health care provider will be blinded to the method of closure. Additional topical or injected anesthetics or the use of sedation will be left up to the patient/parent and provider's discretion. After the procedure, both patient (if older than 3 years old) and parent/guardian will be asked to fill out a short questionnaire (Questionnaires, see Appendix VI). The parent/guardian will be asked to rate the appearance of 3 images of random scars. All parents/guardians in the study will rate the same 3 scars to establish a baseline for each parent. The health care provider will also be asked to fill out a short questionnaire (Questionnaires, see Appendix VI). Upon discharge, the participant and their parent/guardian will be provided with verbal and written return precautions by the study staff (Care Instructions, see Appendix V).

Parents/guardians will be called 3 months after their initial visit for a brief over-the-phone interview (Questionnaires, see Appendix VI). At this time, they will be prompted to take a picture of the scar and send it to the Investigator by e-mail. A Vanderbilt email address has been set-up and is secure per Vanderbilt criteria. As an alternative, they can come back to the VCH ED where study staff will ask them a couple of questions in person and take a picture of the scar.

Every effort will be made to de-identify the images of the scar (using image editing software to crop everything on the image but the scar with some surrounding skin). The images will then be collected and presented to two Plastic Surgeons who will be blinded to the method of closure. They will subsequently score the scar as seen in the images (Questionnaires, see Appendix VI). All data will be collected on paper and then transferred to REDCap®. Each piece of data will be transferred to REDCap® by two study staff independently and then examined for any differences which can be reconciled by examining the paper forms. This will prevent errors in transferring data from paper to electronic format.

Participants will be compensated with a \$15 check after completion of the 3 month questionnaire and sending of photo.

Randomization

Randomization will be accomplished using randomizer.org software to generate a set of 90 numbers from 1 to 3 for 90 enrolled participants. Each digit from 1 to 3 will correspond to a study arm.

Data Acquisition

Study data will be acquired through the means of the aforementioned questionnaires (Questionnaires, see Appendix VI), phone interviews, and by simple chart review. The secondary outcome of "cost of visit" will be acquired through Medical Records.

Institution/Hospital: Vanderbilt Children's Hospital

VIII. Predictor Variables

Predictor variables are the 3 treatment allocation arms: Dermabond[™], Steri-Strips[™], and absorbable sutures. Other independent variables to be collected include demographics of the patient (age, sex, race/ethnicity), specifics of the laceration (location, length and width, time between trauma and wound closure) and level of training of the provider who will be closing the wound. Demographics will be extracted from the patient Electronic Medical Record and from the parent Questionnaire (Questionnaires, see Appendix VI). Both the specifics of the laceration and the level of training of the provider will be extracted from the provider questionnaire at the time of the procedure (Questionnaires, see Appendix VI).

IX. Outcome Variables

a. Primary outcome variable

The primary outcome will be cosmesis of the resultant scar as measured on a 100 mm Visual Analogue Scale where a score of 0 corresponds to "worst scar" and a score of 100 corresponds to "best scar." This scale has been validated as a scoring method to evaluate cosmesis of a scar. 12, 16, 17, 23, 32 Due to its sensitivity and the fact that it provides parametric data, the scale allows for smaller, more practical sample sizes to show clinically-significant differences in populations. 12, 16, 17, 23, 32 The Visual Analogue Scale will be used by two Plastic Surgeons blinded to closure method to rate a patient's scar at 3 months. In addition, parents will be asked to rate the scar on a scale of 0 to 100 during their over-the-phone interview at 3 months. We will compare their rating of their child's scar to the average of their ratings of the 3 images of random scars at the initial visit.

b. Secondary outcome variables

i. Pain experienced by patient

This secondary outcome will be evaluated by the patient (if age-appropriate), parent and provider at the time of the ER visit (Questionnaires, see Appendix VI). Patients aged 3 to 12 will be asked to rate their pain on a Wong-Baker FACES® Pain Rating Scale (licensing for use in progress). Patients aged 12 to 18 will be asked to rate their pain using a 100 mm Visual Analogue Scale with a score of 0 corresponding to "No pain" and a score of 100 corresponding to "Terrible pain." Parents and providers will each be asked to score how much pain they felt the patient experienced on the same Visual Analogue Scale.

ii. Need for anesthetics/anxiolytics/sedation

This secondary outcome examines the need for adjuncts to control pain/anxiety including LET, injected lidocaine, anxiolytics or systemic pain medications, ketamine sedation or others. Data will be collected by study staff observing the procedure. Data will also be extracted from the patient's Electronic Medical Record.

iii. Length of procedure

This secondary outcome, measured in minutes, will be collected by study staff observing the procedure.

iv. Cost of visit

This data will be extracted from the patient's Electronic Medical Records and from the Billing Department.

v. Length of ER stay

This data will be extracted from the patient's Electronic Medical Records.

vi. Resource utilization

Institution/Hospital: Vanderbilt Children's Hospital

This secondary outcome examines the need for personnel in the room to keep the child calm or still. This data will be collected by study staff observing the procedure.

vii. Likelihood that parent would recommend wound closure type

This secondary outcome will be measured using a 100 mm Visual Analogue Scale with a score of 0 corresponding to "Extremely unlikely" and a score of 100 corresponding to "Extremely likely." This data will be extracted from the parent questionnaire at the time of the ED visit (Questionnaires, see Appendix VI).

viii. Complications

Prevalence of complications (infection, dehiscence, etc.) will be evaluated. This secondary outcome will be obtained during the brief phone questionnaire with parents at 3 months after the ED visit (Questionnaires, see Appendix VI).

ix. Poor cosmetic outcome

This secondary outcome will be extracted from the Visual Analogue Scales used to rate a patient's scar, as evaluated by both the parent and Plastic Surgeons blinded to method of closure (Questionnaires, see Appendix VI). A score less than 35 mm on the 100 mm scale will be considered "poor cosmetic outcome" as used in previous studies.

x. Presence of train tracks

This secondary outcome will be extracted from the Plastic Surgeon questionnaire at 3 months (Questionnaires, see Appendix VI).

X. Ethical Considerations

DermabondTM and Steri-StripsTM are both FDA-approved methods of laceration closure and there have been no studies demonstrating the inferiority of these closure methods compared to sutures, the traditional method of laceration closure. Thus, randomizing patients to either DermabondTM or Steri-StripsTM treatment arms does not violate the principle of equipoise.

XI. Risks of Study Participation

Surveillance for medical risks, including but not limited to infection and dehiscence, will be performed during the study of each subject by [name] [name].

The specific aim of this study involves the collection of Personal Health Information (PHI). HIPAA regulations pertaining to subjects' PHI will be reviewed with the Vanderbilt IRB and assurance of conformity to these regulations and protection of PHI provided. As noted, we are taking steps to protect this information. Study staff are required to honor and preserve patient confidentiality and privacy at all times and in all management of data and data files. All completed subject information forms will be initially placed in a locked box in the VCH ED after enrollment and data collection. Forms will then be promptly transferred to individual patient files and maintained in a locked data collection box in a locked office in order to maintain confidentiality and security of data. Photos will be e-mailed to a secure Vanderbilt e-mail. Access to computer files will be further restricted by file passwords. The database will be maintained on REDCap®.

XII. Reporting of Adverse Events or Unanticipated Problems involving Risk to Subjects or Others

Any unexpected problems involving risks to subjects or others will be immediately reported to the Institutional Review Board of Vanderbilt University within ten days using the IRB form #1105.

XIII. Study Withdrawal or Discontinuation

Patients and their parent/guardian(s) will be told very explicitly by the investigators that their participation in this research investigation is entirely voluntary and that they may withdraw at any time. We will further emphasize verbally and in the informed consent document that a decision on the part of the patient or parent/guardian(s) to not participate will in no way change, compromise or jeopardize the patient's care. Indeed, we anticipate that a number of eligible patients will not be enrolled on this basis.

XIV. Data Management

Participants' information (Subject Enrollment Form, see Appendix II, Questionnaires, see Appendix VI, pictures) will be kept in a separate file for each subject. Data will be transferred to the REDCap® server. This data will then be sent for statistical analysis.

XV. Statistical Considerations

We are planning a study of a continuous response variable from independent control and experimental subjects with 1 control per experimental subject. In previous studies, the response within each subject group was normally distributed with a standard deviation of 15 mm on a 100 mm Visual Analogue Scale and the minimal clinically important difference between two scars was 15 mm on a 100 mm Visual Analogue Scale. We performed multiple sample size power calculations using STATA® 14.1 (College Station, Texas). Using one-way ANOVA, with a power of 90% and an alpha of 0.05, we would need between 5 and 21 subjects per group to detect a clinically significant difference of 5 to 15 mm between groups depending on the standard deviation in each group (in anticipation of the fact that we may have a larger standard deviation). In order to assure an effective sample size after accounting for dropouts and missing data, we propose to recruit 30 experimental subject per treatment arm and 30 control subjects, for a total of 90 subjects.

XVI. Privacy and Confidentiality Issues

After the parents have signed the consent form, and the patient has signed the assent form as applicable, one copy will be given to the parents and one copy will be kept by [name] [name] in a locked data collection box in a locked office. All efforts, within reason, will be made to keep protected health information (PHI) private. PHI is health information that is or has been gathered or kept by Vanderbilt as a result of a subject's healthcare. This includes data gathered for research studies, and can be traced back to the subject. Using or sharing ("disclosure") such data must follow federal privacy rules. By signing the consent for this study, subjects are agreeing ("authorization") to the uses and possible sharing of PHI. If a patient or their parent/guardian decides to be in this research study, he/she is also agreeing to let the study team use and share PHI as described below.

As part of the study, [name] [name] and her study team may share the results of a subjects' study-linked questionnaires and photos, as well as parts of the medical

record, to the groups named below. These groups may include people from the Federal Government Office for Human Research Protections, the Vanderbilt University Institutional Review Board, and insurance companies for billing purposes. Federal privacy rules may not apply to these groups; they have their own rules and codes to assure that all efforts, within reason, will be made to keep PHI private.

[name] [name] may give health data, without a subject's name, to others or use it for other research projects. Vanderbilt and [name] [name] and her staff will keep each subject's PHI in strict confidence, and will comply with any and all laws regarding the privacy of such information.

XVII. Follow-up and Record Retention

Research data will not be kept in a subject's medical record. Deidentified study results will be kept for up to 5 years after the study is finished but all identifying data will be destroyed once the study is finished.

XVIII. Data Safety and Monitoring Plan

Surveillance for medical risks, including but not limited to infection and dehiscence, will be performed during the study of each subject by the study investigators. Any adverse events will be reported as per IRB guidelines.

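### The cosmetic hypothesis is equivalence to sutures, but the only named method is a one-way ANOVA sized to detect a difference, with no margin, adhesive-versus-suture contrast or rule for concluding equivalence

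*Combined protocol and SAP*

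**What the plan says.** Two cosmetic questions stand side by side in Section I. The Specific Aim is "to determine the best of 3 different methods of closure of simple pediatric lacerations". The Hypothesis is that either adhesive "will provide clinically equivalent cosmetic outcomes to absorbable sutures". Nothing says which is primary.

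Section II gives the primary analysis in one sentence: "We will examine the association between closure method and the primary outcome variable, cosmesis of the resultant scar". It then anticipates that the adhesive arms "will demonstrate no clinically significant difference in cosmetic outcomes". Section IX defines the scale, the raters and the 3-month time point, but no between-arm test.

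Section XV is the only statistical section. It names one method, inside the sample-size calculation: "Using one-way ANOVA, with a power of 90% and an alpha of 0.05". It reports from earlier studies an SD of 15 mm and that "the minimal clinically important difference between two scars was 15 mm on a 100 mm Visual Analogue Scale". The calculation, however, was run "to detect a clinically significant difference of 5 to 15 mm between groups depending on the standard deviation in each group", giving 5 to 21 subjects per group. Enrolment is then raised: "after accounting for dropouts and missing data, we propose to recruit 30 experimental subject per treatment arm and 30 control subjects". No dropout rate is given, and the SDs tried other than 15 mm are not listed.

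**The concern.** A test of difference and a claim of equivalence need different decision rules. A non-significant F test may mean that the arms are alike, or that the trial was too small or too noisy to separate them. A significant F test says that some arms differ. It does not say which adhesive differs from sutures, by how much, or whether the gap matters clinically.

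The protocol does not say that non-significance will be read as equivalence, but it offers no other route to that conclusion. The risk is that a closure with a clinically worse scar is reported as equivalent, with an error rate nobody chose. That rate grows as the SD rises or photographs are lost, and Section XV anticipates a larger SD, dropouts and missing data.

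The margin is also open. Section XV states a 15 mm minimal clinically important difference (MCID) but applies the label of clinical significance to anything from 5 to 15 mm. A margin chosen after the data could decide the result.

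**Working it through.** **Inputs.** From Section XV: SD 15 mm, MCID 15 mm, alpha 0.05, power 90%, 30 per arm, and 21 per group as the top of the stated range. My assumptions: SDs of 20 and 25 mm, and 21 evaluable per arm, which implies a loss of 1 − 21/30 = 30%.

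**1. The plan's own figure.** For a three-arm ANOVA with n per arm, the noncentrality is λ = n·Σ(μᵢ − μ̄)²/SD², on 2 and 3(n−1) degrees of freedom. With one arm 15 mm from the other two, Σ(μᵢ − μ̄)² = 10² + 5² + 5² = 150. At SD 15 and n = 21, λ = 21 × 150/225 = 14 and power is 91.5%; at n = 20 it is just under 90%. This reproduces the 21. The 5 is reproduced at 15 mm with SD 5 and evenly spaced means. At SD 15, a single-arm difference of 10 mm would need 44 per arm and 5 mm would need 172. The calculation is therefore one of detecting a difference, and at the stated SD it supports only the 15 mm end.

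**2. How often the ANOVA is non-significant when one arm is truly 15 mm worse** (exact noncentral F; critical F 3.10 at n = 30 and 3.15 at n = 21):

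| True means (mm) | n per arm | SD 15 | SD 20 | SD 25 |
|---|---|---|---|---|
| −15, 0, 0 | 30 | 1.8% (λ = 20) | 15% (λ = 11.25) | 35% (λ = 7.2) |
| −15, 0, 0 | 21 | 8.5% (λ = 14) | 31% (λ = 7.875) | 51% (λ = 5.04) |
| −15, −7.5, 0 | 30 | 6% | 27% | 48% |
| −15, −7.5, 0 | 21 | 19% | 45% | 62% |

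**3. The other direction.** Suppose the adhesives are truly +8 and −8 mm from sutures (my assumption), both inside 15 mm. Then λ = 30 × (64 + 0 + 64)/225 = 17.1, and the ANOVA is significant in 96% of trials. A significant result does not refute equivalence to sutures.

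**4. A rule that does answer the hypothesis.** Declare an adhesive equivalent if the 90% confidence interval for adhesive minus sutures lies within ±margin. The half-width is t(0.95; 3(n−1))·SD·√(2/n). At SD 15:
- n = 30: 1.663 × 15 × √(2/30) = 6.44 mm
- n = 21: 1.671 × 15 × √(2/21) = 7.73 mm

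For an adhesive truly 15 mm worse and a 15 mm margin, false equivalence is 3.6% to 5.0% across SD 15 to 25 and both sample sizes.

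Power with no true difference (one adhesive / both adhesives):

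| Margin | SD | n = 21 | n = 30 |
|---|---|---|---|
| 15 mm | 15 | 88% / 79% | 97% / 95% |
| 15 mm | 20 | 55% / 34% | 78% / 64% |
| 15 mm | 25 | 22% / 7% | 49% / 27% |
| 10 mm | 15 | 38% / 17% | 64% / 45% |
| 5 mm | 15 | about 0% | about 0% |

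The 5 mm margin is smaller than the typical half-width, so that interval can almost never fit inside it. If an adhesive is truly 5 mm worse, power for it at a 15 mm margin and SD 15 is 68% (n = 21) to 82% (n = 30).

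**The case against.** The strongest reply is that the pieces are nearly all there. Section XV gives a 15 mm MCID, which beside the wording of Sections I and II implies a threshold. Its 5 to 15 mm phrase can be read as a list of sample-size scenarios, not a second MCID. Sutures are labelled the control arm, so the direction of comparison is indicated. The ANOVA is a reasonable first step for the aim of finding the best method. At the plan's own SD and MCID, its miss rate with one arm worse is 1.8% to 8.5%, inside the 10% that 90% power allows. The larger rates need SDs and losses that the documents do not state.

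Much of this is fair as description. At the design point the practical risk is small, and the higher rates are sensitivity cases, although Section XV itself expects a larger SD and missing data. It does not close the gap. The 15 mm figure is never made a margin, and no contrast or interval rule applies it. An ANOVA that suits the best-method aim still leaves the equivalence hypothesis without an analysis.

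A further point concerns the remedy. Testing each adhesive at 5% controls error per adhesive only. If both were truly 15 mm worse, at least one would be declared equivalent in about 8.8% of trials at SD 15. That is defensible for two separate claims, but the plan should say so. Splitting alpha would lower one-adhesive power at SD 15 and a 15 mm margin from 97% to 94% (n = 30) and from 88% to 78% (n = 21).

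**Conclusion.** The concern holds. Followed as written, the plan cannot establish its cosmetic hypothesis: the only named test addresses a different question, and no margin, contrast or decision rule is specified. This should be corrected before the data are analysed.

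The finding is not that 90 children are too few in every case. The sample is adequate for equivalence with a margin near 15 mm, an SD near 15 mm and little loss. It is inadequate at a 10 mm margin, and cannot succeed at 5 mm. The logical gap does not depend on any assumed figure. The size of the error does: it rests on normal data with equal SDs, on my SDs of 20 and 25 mm, on the assumed 30% loss and on the chosen patterns of means.

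**What to change.** - **Objective (Sections I and II).** State whether equivalence or finding the best method is the primary cosmetic question. Keep the other as a separate, secondary analysis.
- **If equivalence is primary (Section XV).** Pre-specify two contrasts, Dermabond minus sutures and Steri-Strips minus sutures, each with a 90% confidence interval (two one-sided tests at 5%). Conclude equivalence for an adhesive only if its interval lies wholly within the margin. Say that the two claims are separate and each is tested at 5%, or specify a multiplicity adjustment.
- **Margin.** State one and justify it. The 15 mm MCID is the natural candidate, once reconciled with the text that applies clinical significance to 5 to 15 mm.
- **ANOVA.** State that a non-significant result will not be read as equivalence.
- **Power.** Replace the difference-detection statement with equivalence power at the chosen margin, for 30 per arm and for the expected evaluable number, across plausible SDs.

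The cost is wording in three sections and a recalculated power statement, with no extra patients or data to adopt the rule. The downside is that it exposes how much depends on the margin and SD. At 30 per arm, an SD of 20 mm with a 15 mm margin gives 78% power for one adhesive and 64% for both. A 10 mm margin at SD 15 gives 64% and 45%. In either case the trial would have to accept lower power or enrol more children.

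### Patient and parent pain are rated only after the unblinded closure; one pre-closure rating used as a covariate would reduce, though not remove, the noise in the pain comparison

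*Combined protocol and SAP*

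**What the plan says.** Section II (Summary of Approach) states the expectation that the two adhesive arms will do no worse cosmetically while "reducing the pain experienced by patients during laceration closure". Pain is listed first in the secondary aim and first among the secondary outcomes.

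On timing, Section VII (Study Design) says: "After the procedure, both patient (if older than 3 years old) and parent/guardian will be asked to fill out a short questionnaire". Section IX.b.i says that pain "will be evaluated by the patient (if age-appropriate), parent and provider at the time of the ER visit", which names the visit but no rating before closure. The content of the proxy rating is retrospective: "Parents and providers will each be asked to score how much pain they felt the patient experienced on the same Visual Analogue Scale".

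Self-report uses two instruments: "Patients aged 3 to 12 will be asked to rate their pain on a Wong-Baker FACES® Pain Rating Scale" and "Patients aged 12 to 18 will be asked to rate their pain using a 100 mm Visual Analogue Scale". Age 12 falls in both bands.

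Besides arm and demographics, Section VIII (Predictor Variables) lists "specifics of the laceration (location, length and width, time between trauma and wound closure) and level of training of the provider". Pre-closure pain is not among the variables. The only rating described as a baseline is the parent's scoring of three standard scar images, which serves cosmesis. Section VII also states that patient, parent and provider all know the closure method. Section XV gives no SD, target difference or analysis model for pain.

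**The concern.** Eligible children range from newborns to 17-year-olds, with wounds up to 12 hours old. They will differ in how much they hurt before anyone touches the wound, and parents will differ in where they place the same pain on a 100 mm line. With a single score per rater, taken afterwards, all of that variation sits in the between-arm comparison, and chance imbalance in pain on arrival cannot be seen or adjusted for.

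The protocol accepts this reasoning for cosmesis, where each parent's later scar rating is set against that parent's own ratings of the standard images. Pain, scored by the same parents, has no counterpart.

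At stake is the precision of one secondary outcome that is part of the study hypothesis. A pre-closure rating cannot be recovered once the wound is closed.

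**Working it through.** **The plan's own figure.** Section XV states 5 to 21 subjects per group at 90% power and alpha 0.05, for cosmesis. Both ends can be reproduced with one-way ANOVA: a 15 mm difference with SD 15 and one group differing gives 21 per group; 15 mm with SD 5 and evenly spread means gives 5. No figure is given for pain, so there is none to reproduce.

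**Inputs for pain.**
- About 30 per arm (Section XV).
- Assumed, not in the documents: parent VAS SD 25 mm; true difference 15 mm; r from 0.2 to 0.6; one pairwise comparison, two-sided 5%, no multiplicity adjustment.

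**Formulas.** ANCOVA residual SD = 25 × √(1 − r²). Noncentrality = 15 / (residual SD × √(2/30)). Power comes from the two-sample t-test with 58 degrees of freedom (critical value 2.00). The equivalent increase in sample size is 1/(1 − r²).

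Worked cases:
- Unadjusted: standard error 25 × √(2/30) = 6.45; 15/6.45 = 2.32; power 63%.
- r = 0.5: residual SD 25 × √0.75 = 21.65; noncentrality 2.68; power 75%.

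| r | Variance left | Equivalent extra children | Power |
|---|---|---|---|
| none | 100% | – | 63% |
| 0.2 | 96% | 4% | 65% |
| 0.3 | 91% | 10% | 67% |
| 0.4 | 84% | 19% | 70% |
| 0.5 | 75% | 33% | 75% |
| 0.6 | 64% | 56% | 81% |

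Taking one degree of freedom for the covariate moves each power by less than 0.1 percentage point. Estimating the slope in a three-arm model inflates variance by about 1/(90 − 3 − 2) = 1.2%. At r = 0.1 this cancels the benefit: 0.99 × 1.012 = 1.002.

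**Sensitivity to the SD.** At r = 0.5 and a 15 mm difference, power goes from 81% to 91% with SD 20, and from 48% to 59% with SD 30.

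**Why not a change score.** With equal SDs before and after, its variance is 2(1 − r) times the unadjusted variance: 160% at r = 0.2, 140% at r = 0.3 and 100% at r = 0.5. It helps only when r exceeds 0.5.

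**Self-report.** Section III cites 74.1% of lacerations in children under 6. If enrolment followed that, 25.9% × 30 ≈ 8 per arm would be 6 or older, and the adolescents using the VAS are only a part of those. The youngest children cannot self-report, and the rest are split over two scales. No gain is computed here for self-report.

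**The case against.** The strongest reply is that this is a preference for precision and not an error. Randomisation makes pre-closure differences a matter of chance, so a post-closure comparison is valid in that respect. That stands.

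The benefit also depends wholly on r, and the design gives reason to expect a modest value. A rating at rest captures wound pain; the outcome is recalled procedural pain after LET, wash-out and discretionary further anesthesia or sedation. This stands too, and is why the range starts at r = 0.2, where the gain is about two points of power.

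Third, age and wound characteristics are already collected. If the pain model adjusted for them, the further gain would depend on the partial correlation and could be smaller. The plan states no pain model, so this is neither planned nor excluded.

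Finally, the data form and questionnaires (Appendices III and VI) are not in the available text. A question about earlier pain could exist there, but in a questionnaire completed after closure it would be retrospective and answered by someone who knows the arm.

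A reader might infer more than this: that one rating would remove the noise, that it would account for distress, or that it would correct rating bias from unblinded raters. None of these is supported. Adjustment removes only the share r². A pain item does not measure fear or distress. A baseline leaves later ratings just as open to knowledge of the arm.

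**Conclusion.** The point holds as a cheap gain in precision for a secondary outcome. The available text places patient and parent pain ratings after closure and plans none before it, so pre-existing differences between children, and in parents' use of the scale, add noise to the pain comparison. The absence of a baseline does not by itself bias that comparison.

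The size is conditional. Under the assumed SD and difference, the parent-score comparison moves from 63% power to between 65% and 81% over r = 0.2 to 0.6. The SD, the difference and r are all assumptions. For self-report the gain is uncertain. The provider's score is unchanged by the proposal, and the primary cosmesis outcome is unaffected.

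**What to change.** - After consent, at one fixed time before LET and before the arm is revealed, have the parent (all ages) rate the child's current pain on the 100 mm VAS. Children old enough to self-report rate it on the scale they will use later. The protocol should settle which scale applies at age 12.
- State when the arm is revealed relative to consent and LET; the text does not say.
- Prespecify ANCOVA of post-closure pain on arm and that rater's own pre-closure score, not a change score, and within scale for self-report.

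Cost: one added item, about a minute per family, and one line of analysis, using staff who are already with the family at consent. The downside is slightly more questionnaire burden and little return if r proves low.
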